Specific Aim 2 is to test the hypothesis: the cumulative mean (discounted) total health care costs post-intervention will differ between intervention groups. As described in the protocol synopsis, health care costs during the intervention phase of the Look AHEAD have been published (Espeland, 2104). We have continued to collect these data post-intervention (i.e. after 9/2012) and Specific Aim 2 is based on these data as collected through 7/2020. Each participant’s annual costs for hospitalizations, outpatient care, medications, and rehabilitation/nursing home stays will be tallied and divided by follow-up times to obtain observed costs per year. Weighted analysis of covariance will be used to compare intervention groups, with analytical weights proportional to participants’ lengths of follow-up. Clinic, the sole stratification factor in randomization, will be used as a covariate. To accumulate costs post-intervention, annual estimates will be discounted at 3% per year and summed and bootstrapping will be used for confidence intervals of accumulated mean costs. We will also

generate accumulated mean costs across the full span of follow-up (i.e. since randomization) for descriptive purposes.

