5.2 Specific Aim 2 (primary) is to test the hypothesis: the cumulative mean (discounted) total health care costs post-intervention will differ between intervention groups. As described in the protocol synopsis, health care costs during the intervention phase of the LA trial have been published [Espeland, 2104]. We have continued to collect these data post-intervention (i.e. after 9/2012) and Specific Aim 2 is based on these data as collected through 7/2020. Each participant's annual costs for hospitalizations, outpatient care, medications, and rehabilitation/nursing home stays will be tallied and divided by follow-up times to obtain observed costs per year. Weighted analysis of covariance will be used to compare intervention groups, with analytical weights proportional to participants' lengths of follow-up. Clinic, the sole stratification factor in randomization, will be used as a covariate. To accumulate costs post-intervention, annual estimates will be discounted at 3% per year and summed and bootstrapping will be used for confidence intervals of accumulated mean costs. We will also generate accumulated mean costs across the full span of follow-up (i.e. since randomization) for descriptive purposes.

Supporting analyses: We will also report whether differences in the separate components of health care costs (hospitalizations, inpatient, medications, other) differ between arms. Other supporting outcomes will be the annual rates of hospitalizations, medication use (by previously reported classes), nursing home stays, and rehabilitation center stays.

Subgroup analyses: Pre-specified subgroup comparisons include sex, history of cardiovascular disease, race/ethnicity, and age. We will report tests of interactions to assess the consistency of differences between intervention groups for each of these subgroups.

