Power: As noted earlier, LA-E plans to follow 3,800 participants through 2020, with regular collection of data towards estimating medical care costs. The hypothesis for this aim also draws from health care costs from the 279 participants who provided data during the post-intervention follow-up but who are not expected to be followed in LA-E. This provides us a range from 1-8 years of post-intervention cost data. Based on the enrollment/retention assumptions (Section 4.3), we estimated the distribution of these follow-up times and used study data and the proposed analytical approach to estimate the standard error for the inference we describe above: this resulted in a standard error of \$196/yr for the difference between intervention groups. Thus, we project (2-sided 0.05 alpha) 80% power to detect a mean difference in annual total health care costs of \$549/yr. We note that the difference during the intervention phase of LA was \$595/yr and increased with the age of participants (i.e. was \$864/yr for participants aged 65-76 at LA entry) [Espeland, 2014].

5.3 Specific Aim 3 (secondary) is to test the hypothesis: among obese and overweight adults with type 2 diabetes, random assignment to an average of 10 years of ILI relative to DSE will lower the prevalence of frailty seen during LA-E.

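### The co-primary cost test compares dollars per observed year, while its hypothesis is about cumulative discounted cost, and the accumulation step does not say how death and censoring enter

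*Combined protocol and SAP*

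**What the plan says.** SAP 5.2 states the hypothesis that "the cumulative mean (discounted) total health care costs post-intervention will differ between intervention groups". Each participant's costs are then "tallied and divided by follow-up times to obtain observed costs per year. Weighted analysis of covariance will be used to compare intervention groups", with weights proportional to length of follow-up and clinic as covariate. Protocol 1.5 gives the same method: "Weighted analysis of covariance will be used to compare intervention groups, with analytical weights proportional to" follow-up length.

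Discounting appears only in a later step: "annual estimates will be discounted at 3% per year and summed and bootstrapping will be used for confidence intervals of accumulated mean costs". No test is attached to that step. The annual estimates it sums are not defined, and neither death nor loss to follow-up is mentioned.

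The power paragraph of SAP 5.2 is on the annual scale. It gives a standard error, in dollars, of "196/yr for the difference between intervention groups" and a detectable difference of $549/yr at 80% power.

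Three other places bear on this:
- SAP 4.2 notes about 40 more deaths in DSE, and says mortality may need exploring as informative missingness if the imbalance grows.
- SAP 4.4 plans inverse probability weighting as a sensitivity analysis for survival outcomes.
- SAP 5.1 powers total mortality for a 20% effect in future data.

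**The concern.** Cost per observed year and cumulative cost over a fixed window are different quantities when the arms differ in survival. A participant who lives longer adds dollars to the numerator and years to the denominator, so the extra years leave the rate nearly unchanged although the payer has paid for them. Longer life is the other co-primary aim. Success on that aim would therefore move the cost test, relative to the cost hypothesis, toward a finding of reduced cost.

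The p-value and the cumulative interval also come from different estimators, and nothing says which governs if they disagree.

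**Working it through.** **1. The plan's own figure.** (1.960 + 0.842) x $196 = $549/yr, which reproduces the stated value. The test is therefore powered on an annual rate.

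**2. What the test estimates.** For participant i with cost C_i and follow-up T_i, the weighted mean in an arm (clinic aside) is sum[T_i x (C_i/T_i)] / sum T_i = sum C_i / sum T_i, that is, total dollars over total person-years. Write R for this rate and, from here, C and T for mean cost and mean follow-up per person. Then C = R x T and

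(C_ILI - C_DSE)/T_DSE = (R_ILI - R_DSE) + R_ILI x (T_ILI - T_DSE)/T_DSE.

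The planned test sees only the first term. The second is positive whenever ILI has more follow-up because of fewer deaths.

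**3. Inputs.**
- From the documents: 9/2012 to 7/2020 is 94 months, or 7.83 years; discount rate 3% (ln 1.03 = 0.02956); mortality effect 20%, taken as a hazard ratio (HR) of 0.80.
- Not in the documents, so assumed: cost per year alive, cost at death, and DSE mortality after 9/2012.
- A rough ceiling on mortality: 1:1 randomization of 5,145 gives about 2,572 in DSE, and 509 DSE deaths are projected since randomization. Mortality after 9/2012 is then at most about 509/2,572 = 19.8%, setting aside deaths that are never ascertained.

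**4. Worked example.** Assume a constant DSE death rate of 2%/yr (14.5% over the window), 1.6%/yr in ILI, and $10,000 per year alive in both arms with no cost at death. Discounted years alive are (1 - exp[-(h + 0.02956) x 7.833]) / (h + 0.02956).
- DSE: 6.492. ILI: 6.588. Difference: 0.096 years.
- Rate difference: $0. Discounted cumulative difference: $10,000 x 0.0961 = $961 higher in ILI.
- Break-even: ILI would have to cost $961/6.588 = $146/yr less while alive just to match DSE cumulatively. That is 27% of $549 and 0.74 of the $196 standard error.
- If ILI really saved $549/yr, the rate times 6.99 discounted years would show -$3,839. The cumulative difference would be $9,451 x 6.588 - $10,000 x 6.492 = about -$2,656.

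**5. Range.** The gap is the discounted cumulative difference minus the rate difference times 6.99 years.

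| Assumptions | HR 0.80 | HR 0.90 |
|---|---|---|
| 12.3% DSE mortality, rising (Gompertz) hazard, $6,000-14,000/yr, $0-40,000 at death | $433-1,109 | $216-555 |
| 2%/yr, $5,000-15,000/yr, none at death | $481-1,442 | $239-717 |
| 3%/yr (20.9%, just above the ceiling), $5,000-15,000/yr, none at death | $689-2,067 | $342-1,026 |

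For scale, $549/yr x 6.99 = $3,839, so the first row at HR 0.80 is 11-29% of the detectable difference carried to the cumulative scale.

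**6. The accumulated figure.** Two readings are possible. If the annual estimates are means among those still observed, the sum describes someone who survives the whole window and has the same tilt. If years after death enter as zero, the sum already reflects survival, and only loss to follow-up remains to be handled. The text does not decide between them.

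**The case against.** Cost per observed year is a legitimate payer quantity, and the plan does report accumulated discounted means with intervals, so a reader would see the cumulative result. SAP 4.2 and 4.4 show awareness of mortality and missing data. All this stands, but none of it puts a test on the hypothesis as stated, and the weighting in 4.4 is not for costs. The plan also does not say outright that cost follow-up ends at death. That is the natural reading of dividing by follow-up time, and it needs stating.

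A reader might go further and infer that the plan sums costs without survival weighting, so that both figures are wrong by design. The documents do not support that: they leave the annual estimates undefined, which is under-specification. Nor does the lack of discounting in the test matter much by itself, since it scales both arms and the standard error similarly.

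A reader might also infer that the trial would falsely claim savings. An opposite sign is possible: at $10,000/yr, $20,000 at death, HR 0.80 and 12.3% mortality, the rate difference is -$66/yr (about -$460 accumulated) against a cumulative difference of about +$310. But -$66/$196 is -0.34 standard errors. The chance of a significant result favouring ILI is then about 5%, against a nominal 2.5%, and about 10% with $40,000 at death. With no extra cost at death it stays at 2.5%. At $6,000/yr and $40,000 at death, ILI is cheaper cumulatively as well (about -$390).

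**Conclusion.** The mismatch is real and needs no assumption: the hypothesis is cumulative and discounted, while the test and its power are on cost per observed year. The direction, relative to the hypothesis, follows from the algebra: toward the arm with longer survival. That this would be ILI is suggested by the excess of about 40 DSE deaths, which SAP 4.2 calls slight, and by the powered 20% effect. It is not established.

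The size depends on assumed costs, mortality and hazard ratio. At HR 0.80 with 12% mortality it is about $430-1,110 per person, and about half that at 0.90. This is enough to matter beside the detectable difference, but it does not show that a false claim is likely. For the accumulated figure, the finding is only that its treatment of death and censoring is unstated.

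**What to change.** In SAP 5.2 and protocol 1.5:
- Make the primary estimate the difference in mean cumulative discounted cost from 9/2012 to 7/2020.
- Define follow-up for costs and set cost to zero after death.
- Handle loss to follow-up in one stated way: either inverse-probability-of-censoring weights, or annual means among those alive and observed multiplied by Kaplan-Meier survival, then discounted and summed.
- Take both the p-value and the confidence interval from one bootstrap stratified by clinic.
- Keep the weighted ANCOVA of dollars per year as a supporting analysis.
- Restate the detectable difference on the cumulative scale.

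This uses data already being collected. It costs wording and some programming. The stated detectable difference may become less favourable; the standard error on the cumulative scale cannot be derived from the documents and would have to be estimated from study data, as the $196/yr was.

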Frailty is the primary outcome for this aim and is a new aim because it has not been measured prior to LA-E. It will be assessed using the Fried criteria [Fried, 2001] developed during the Cardiovascular Health Study. Frailty classification is based on the presence of five frailty characteristics: 1) walking speed standardized based on median height and sex, 2) grip strength standardized based on body mass index (BMI) and sex, 3) energy expenditure standardized based on sex, 4) exhaustion based on self-report, and 5) weight loss of 10 lbs or more in the last year without trying or intending to (based on self-report). Walking speed will be assessed using the timed short walk included in the Short Physical Performance Battery (SPPB) and grip strength. Energy expenditure will be based on kcal/week of energy derived from the Paffenbarger physical activity questionnaire. Exhaustion will be assessed using the question from the Geriatric Depression Scale, "Do you feel full of energy?." Weight loss will be assessed by self-report. (We acknowledge that this is a difficult item to interpret for the LA cohort, and will also examine the impact on a construct without this item.) Based on these assessments, frailty will be classified into three stages: non-frail (no frailty characteristics present), pre-frail (1 or 2 frailty characteristics present), and frail (3 or more frailty characteristics present). Our primary analysis will classify a person as having prevalent frailty if they are classified as frail during either of the LA-E visits. The proportion of participants experiencing any frailty will be compared between randomized groups using logistic regression, with clinic site, sex, and time from randomization to classification of frailty or the last non-frail classification as covariates. Odds ratios and 95% confidence intervals will be used to summarize the relative effect of the intervention on frailty.

Supporting analyses: include persistent major mobility disability (PMMD) based on repeated assessments of the adjudicated 400-m walk, sensitivity analyses for frailty and PMMD, falls, fractures, SPPB, grip strength, and Pepper Assessment Tool for Disability (PAT-D).

PMMD is considered present when an individual fails to complete two successive 400-m walks [Newman, 2006; Pahor, 2014]. Death after an initial MMD determination will also be considered

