PMMD. Additionally, information used in the adjudication of MMD (i.e. self- or proxy report of inability to walk across a small room without the assistance of another person) in the absence of 400-m walk data will be collected every 6-months via telephone and will be used to ascertain PMMD. We will define PMMD based on the sequence of 400-m walks from LA-C (one) and LA-E (twice). In addition, those who failed the 400-m walk for the first time at their last scheduled LA-E clinic visit and who are not adjudicated as persistent failures will return 6 months later for a repeat assessment to establish persistence. The proportion of participants experiencing any PMMD will be compared using logistic regression models. The basic model will include an indicator variable for intervention assignment, follow-up time with covariate adjustment for sex and clinical site. Follow-up time for PMMD will be considered as the time until the initial MMD failure or last successful completion of the 400-m walk for those without PMMD. Odds ratios and 95%CI will be used to summarize the relative effect of the intervention on PMMD.

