Power: If 3800 participants are enrolled in LA-E and 8% in the DSE group will be classified as frail during LA-E, we project 80% power to detect an odds ratio of 0.70 (two-sided 0.05 type 1 error). Note that our preliminary data with a somewhat limited definition of frailty provide support for these assumptions: observed OR=0.75 [95% CI 0.57, 0.98] and 6.4% prevalence in the DSE group.

As noted earlier, LA-E plans to follow 3,800 participants through 2020, with collection of MMD data on two occasions, 2 years apart. If we assume 12.7% of the DSE group experience PMMD, a two-sided 0.05 probability of Type I error, and 1900 active participants in each group are followed for MMD, LA-E will have approximately 80% power to detect a 25% reduction in the

odds of PMMD in the ILI group compared to the DSE group. This percent relative reduction is consistent with what was observed in the LIFE [Pahor, 2014] trial (physical activity vs successful aging interventions) where the physical activity group had a 28% reduction in the hazard rate for PMMD.

5.4 Specific Aim 4 (secondary) is to test the hypothesis: the time until first occurrence of end stage renal disease (RRT or death from nephropathy) post-randomization will differ between intervention groups.

The primary outcome for diabetic nephropathy will be the first occurrence of **end stage renal disease (ESRD)**, defined as renal replacement therapy (RRT) or death from nephropathy. Information on outpatient and inpatient dialysis has been a crucial part of data collection since the beginning of the LA trial and has been collected every 6 months throughout. Renal transplants have been captured throughout follow-up, as well. This will continue in LA-E. The distribution of time to first occurrence of ESRD will be compared between ILI and DSE using survival analyses as described for total mortality (Section 5.1). Because data on ESRD will continue to be collected every six months in LA-E (as it was in LA and LA-C), censoring and follow-up times will cluster around these six month time points even though we will use the dates of the participant encounter to calculate follow-up time. Because 6-month intervals are fairly short and regular in length throughout follow-up, we will follow the commonly accepted recommendations [Leung, 1997] and will not complicate the analysis by considering interval censoring. All data since randomization will be used for analysis.

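### The frailty and mobility-disability logistic models adjust for a time that the outcome partly sets; this can cost power and, if second-exam loss or the effect is uneven, bias the odds ratio.

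*Combined protocol and SAP*

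**What the plan says.** SAP 5.3 (Specific Aim 3, secondary) will "classify a person as having prevalent frailty if they are classified as frail during either of the LA-E visits". The proportions are compared by logistic regression, "with clinic site, sex, and time from randomization to classification of frailty or the last non-frail classification as covariates".

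For the supporting outcome PMMD the same section says: "The basic model will include an indicator variable for intervention assignment, follow-up time with covariate adjustment for sex and clinical site". It then defines that time: "Follow-up time for PMMD will be considered as the time until the initial MMD failure or last successful completion of the 400-m walk". The last successful walk applies to participants who are not cases. The walks used are one from the Continuation and two from the Extension.

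The power paragraph of SAP 5.3 starts from this assumption: "If 3800 participants are enrolled in LA-E and 8% in the DSE group will be classified as frail during LA-E". On that basis, "we project 80% power to detect an odds ratio of 0.70" at two-sided 0.05. For PMMD it assumes 12.7% in DSE, 1,900 per arm and a 25% reduction in the odds, again for about 80% power. Neither statement mentions a follow-up time term.

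**The concern.** The outcome is ever frail versus never frail over two exams. The time covariate depends on which of these happened:

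- frail at exam 1: time to exam 1;
- not frail at exam 1 and absent from exam 2: time to exam 1;
- first frail at exam 2: time to exam 2;
- never frail and seen twice: time to exam 2.

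Cases found before the last exam therefore carry a shorter time than non-cases who complete both exams. A person first frail at exam 2 has the same time as a completer. At short times the model compares people frail at exam 1 with non-frail people who died or missed exam 2. That comparison uses little of the non-frail group, which costs precision. It also depends on how many non-frail people each arm loses between exams. If ILI lowers mortality, as the first primary aim proposes, ILI has fewer such people and looks worse on frailty.

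In the PMMD model the clock stops at the first failed walk for a case but runs to the last successful walk for a non-case, so the same problem arises. At stake is the main analysis of a named secondary aim, and the claim that it has 80% power.

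**Working it through.** **Inputs from the documents.** 3,800 participants, taken as 1,900 per arm (1:1 randomization); DSE frailty 8%, OR 0.70; DSE PMMD 12.7%, OR 0.75; two-sided 0.05 (SAP 5.3). Exams about two years apart (protocol 1.4.4). Loss to follow-up 2% per year (SAP 4.3). A 20% intervention effect on future mortality (SAP 5.1).

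**Assumed, because the documents do not give them.** 5% of DSE frail at exam 1 and 3.5% newly frail at exam 2; 6% two-year DSE mortality; the spread of times from randomization to exam.

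**Step 1. Reproduce the stated power.** Power = Φ[(|p1 − p2| − 1.96·SE0)/SE1], with SE0 = √(2p̄(1 − p̄)/n) and SE1 = √([p1(1 − p1) + p2(1 − p2)]/n).

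- Frailty: ILI odds 0.70 × 0.08/0.92 = 0.0609, so p2 = 0.0574. SE0 = 0.00821 and SE1 = 0.00820. Power = Φ[(0.0226 − 0.0161)/0.00820] = 78.7%.
- PMMD: ILI odds 0.75 × 0.127/0.873 = 0.1091, so p2 = 0.0984. Power = 79.7%.

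Both agree with 80%, and both come from a comparison with no time covariate.

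**Step 2. Limiting case by hand.** Suppose all first exams fall at one time and all second exams two years later. The covariate then has two values and acts as a stratum. Let m be the share of people non-frail at exam 1 who have no exam 2.

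- Short-time stratum: odds of frailty = p1/[(1 − p1)m], so its odds ratio is OR × m(DSE)/m(ILI).
- Long-time stratum: its odds ratio is that for new frailty among exam-2 attendees.

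The adjusted estimate is close to the inverse-variance average of the two log odds ratios.

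*Equal 10% loss, OR 0.70 at both exams.*
- Short-time stratum, frail versus not: DSE 95 versus 180.5, ILI 67.5 versus 183.2; OR 0.70, variance 0.0363.
- Long-time stratum: DSE 56.9 versus 1,567.6, ILI 40.8 versus 1,608.4; OR 0.70, variance 0.0433.
- Combined SE = 1/√(1/0.0363 + 1/0.0433) = 0.141. Power = Φ(0.357/0.141 − 1.96), about 72%.
- Without the covariate: OR 0.696, SE 0.130, power about 79%.

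The odds ratio is essentially unchanged, and about 8 points of power go.

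*Unequal loss.* DSE: 2 × 2% + 6% = 10%. ILI: 2 × 2% + 0.8 × 6% = 8.8%.
- Short-time OR = 0.70 × 10/8.8 = 0.795, variance 0.0371. Long-time OR = 0.70, variance 0.0430.
- Weighted log OR = (26.97 × −0.229 + 23.25 × −0.357)/50.22 = −0.288, so OR 0.75. SE 0.141, power about 53%.
- Without the covariate: OR 0.70, power about 78%.

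**Step 3. Simulation with other exam timings.** 1,900 per arm, clinic omitted. First exams were tightly clustered, on even years, or spread over about four years. The first three rows use the frailty rates above. The fourth varies them: 50–75% of cases found at exam 1 and 3–15% missing exam 2. PMMD used assumed splits of first failures over the three walks.

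| Setting | As written | Comparison model |
|---|---|---|
| Frailty, OR 0.70, equal 10% loss | OR 0.69–0.70; power lower by about 0–8 points | near the stated 80% |
| Frailty, OR 0.70, loss 10% vs 8.8% | OR 0.71–0.75; power 55–76% | power 79–85% (time to exam 1) |
| Frailty, no effect, equal loss | OR about 1.00; type I error about 5% | same |
| Frailty, common OR about 0.70, varied inputs | power lower by 2–8 points (spread) or 4–26 (clustered) | power 76–83% |
| Frailty, effect at exam 1 only | OR about 0.72 (spread), 0.75 (clustered) | OR about 0.71 |
| PMMD, common OR about 0.75 | power 64–69% | power 78–83% |
| PMMD, waning effect | OR 0.78–0.80; power 49–59% | OR 0.75; power 76–78% |

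The hand result for unequal loss sits at the clustered edge of the simulated range, as it should.

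**The case against.** Four points can be made for the plan.

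**Bias is conditional.** With a common odds ratio and equal loss the estimate is not biased and type I error holds. SAP 4.2 and 4.4 describe retention as balanced between arms. This stands. However, SAP 4.2 also reports about 40 more deaths in DSE and foresees that a growing imbalance could make mortality an informative source of missing data. A waning legacy effect is also plausible. The conditions for bias are therefore not remote.

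**The size is uncertain.** It depends mainly on how spread the exam times are. The even-year rule in SAP 3.0 and the exam windows in protocol Table 1 do not settle that. This stands, so only ranges are given. The PMMD figures are the least certain: the simulation does not model the rule that counts death after an initial failure, or the six-monthly telephone ascertainment.

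**Sensitivity analyses exist.** SAP 5.3 adds predictors of missingness and plans multi-state or transitional models with death and loss to follow-up as absorbing states. The latter handle timing properly. But none of them refits the main model without this covariate, and SAP 4.4 gives primary consideration to the original analysis. They reduce the problem without removing it.

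**Larger loss imbalances give alarming results.** A reader might infer severe bias from 12% versus 10% or 13% versus 10% loss. The documents do not support those cases through a 20% lower death rate. A 2-point gap needs 2/0.20 = 10% DSE deaths, leaving 2% for other loss where SAP 4.3 implies 4%. A 3-point gap needs 15% deaths, more than the 13% total, and means 0.03 × 1,900 = 57 extra losses in two years, against about 40 excess deaths in the whole trial to date.

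**Conclusion.** The point holds in a limited form. Both logistic models condition on a post-randomization time that the outcome partly sets, and the 80% power figures describe an analysis without it.

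Under the assumed frailty rates, equal 10% loss costs about 0 to 8 points of power with negligible bias. Loss of 10% versus 8.8% moves a true odds ratio of 0.70 to about 0.71–0.75 and gives power of about 55–76%, against about 79–85% with time to exam 1. These figures rest on the assumed exam-specific rates, 6% two-year DSE mortality and the exam-time spread. An effect that differs by exam can also shift the odds ratio toward the null.

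A reader might infer that the covariate always biases the odds ratio or invalidates the test. It does not: the short-time odds ratio is distorted by the factor m(DSE)/m(ILI), which is 1 when loss is equal. Because the outcome is secondary (PMMD is supporting) and neither primary aim is touched, this is something to fix rather than a bar to the study.

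**What to change.** In the one-record frailty model, replace the covariate with the scheduled time from randomization to exam 1. The outcome does not set this time, it is defined even for someone who attends only exam 2, and it keeps the ever-frail comparison of the Aim 3 hypothesis. For PMMD, likewise use a scheduled time that the outcome does not set. The power statements then match the analyses they describe.

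Add two sensitivity analyses:

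- a person-visit discrete-time logistic model, in which each participant contributes each attended exam until first frail, stating that it estimates the odds of first frailty per exam rather than the ever-frail proportion;
- frailty or death as the outcome.

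The cost is SAP wording and a small code change, with no new data, and it should be done before unblinded analysis. One small downside remains: scheduled time does not adjust for the lesser opportunity to be classified frail among participants who attend only one exam.
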